## **8. TREATMENT OF SUBJECTS**

### **8.1 Informed Consent Form**

An IRB-approved informed consent form (ICF) will be given to each prospective subject before participation in any study procedures. Prospective subjects will be given as much time as needed to read the ICF and will have the opportunity to have any study-related questions answered to their satisfaction prior to signing the ICF. If further questions exist, prospective subjects will be given sufficient time during the visit to have questions regarding the study and/or the ICF answered by the Investigator or study coordinator prior to signing.

### **8.2 Subject Identification**

Enrolled subjects will be assigned a number that will uniquely identify every subject on the study. The numbers will remain with the subject throughout the study and should be used in all references to the individual in this study.

### **8.3 Subject Instructions for the Study**

Subjects will be provided with the following instructions to follow during the study:

#### **8.3.1. Study Product Usage Instructions**

- Apply the provided treatment product liberally to rash area of your child with every diaper change. Reapply as needed throughout the day.
- Subject's parent/legal guardian will complete a daily diary, recording time, number of diaper changes, and number of applications to ensure treatment compliance.

#### **8.3.2. Subject Instructions for Study Visits**

- Subjects must show up to the study site with clean test area.
- Subject's parent/legal guardian must stop using any topical diaper rash treatment products and replace them with the provided study product.
- Bring the test product and daily diary with you to every visit.

### 8.3.3. General Study Instructions

- Throughout the study, parents/legal guardians must ensure subjects to avoid extended periods of sun exposure. Extra care should be taken to wear sunscreen and accessories (i.e., hat) and avoid sun exposure from 10 am to 3 pm.
- Do not use any topical diaper rash and/or moisturizing products on the test area (such as sunscreen, lotion, cream, oil, ointment, wipes), other than the assigned study product, for the duration of the study.
- Do not start using any new body care products other than the provided study product.
- Parents/legal guardians must use the same type of diapers for the duration of the study.

## 9. STUDY PROCEDURES

There will be 3 visits during the course of the study:

1. Visit 1 – Baseline/Day 0
2. Visit 2 – Week 1/Day 7 (follow-up)
3. Visit 3 – Week 3/Day 21 (end of study or EOS)

Protocol GLI.04.US.SL.023

CONFIDENTIAL

**Table 1. Study Visits and Assessments**

Procedure	Visit 1	Visit 2	Visit 3
	Day 0	Week 1 or Day 7	Week 3 or Day 21
	Screening/Baseline	Follow-up	Follow-up
Informed consent	X		
Demographic	X		
Inclusion and exclusion criteria	X		
Concomitant medications	X	X	X
Digital photography	X	X	X
Safety assessment	X	X	X
Efficacy assessment	X	X	X
Self-assessment questionnaire	X*	X	X
Adverse events		X	X
Study product	W/D	I/W/D	I/C/W
Subject diary	D	C/R/D	C/R

\*At home questionnaire after first application.

For products and daily diaries: D=Distribute, C=Collect, R=Review, W=Weigh, and I=Inspect (visually)

Protocol Version: 01

This document contains confidential, proprietary information.

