## 1. SYNOPSIS

Clinical Study Title:	An open-label study to assess efficacy and safety of a Healing Ointment when used on infants with mild-to-moderate diaper rash
Clinical Trial Number:	GLI.04.US.SL.027
Indication:	Dermatitis
Study population:	Infants at 2- <del>24</del> 35 months of age
Country(ies) Involved and Planned Number of Study Centers:	USA Site: Young Skin [name]
Number of Subjects:	30 subjects to complete
Clinical Study Design:	
This is a single-center, open-label study.
 
Subjects and their parent/legal guardians will report to the site at baseline (day 0) visit, will be given an informed consent form, HIPAA form, photography release form, and medical history form to complete.
 
Subjects will be screened on the basis of the selection criteria for study qualification. Efficacy assessment (skin health, skin smoothness, skin texture), tolerability assessment (dryness, peeling, edema), and self-assessment questionnaire will be performed.
 
Subjects' parent/legal guardians will be instructed to apply the provided Healing Ointment to the buttocks and groin area (if applicable) at every diaper change.
 
Subjects and their parent/legal guardians to return to the site at day 7 (<math>\pm</math> 3 days) and day 21 (<math>\pm</math> 3 days) for follow-ups.
 
For each follow-up visit, investigator will perform objective assessments, tolerability assessments, and photography, if consented. Subjects' parent/legal guardians will perform self-assessment questionnaire.
 
A subject and their parent/legal guardian will be involved in the study for 3 weeks.

Primary Effectiveness Objective and Endpoint:	To evaluate efficacy of a Healing Ointment in skin texture and smoothness in infants 2 to <del>24</del> 35 months old with mild to moderate diaper dermatitis

Secondary Effectiveness Objective(s) and Endpoint(s):	To evaluate subject satisfaction using a Self-Assessment Questionnaire.
Safety Objective and Endpoint	To evaluate safety and adverse events (AEs) throughout the study.
Clinical Study Duration:	The planned clinical study duration (from FSFV to LSLV) is approximately 9 weeks. The planned duration of recruitment is approximately 6 weeks.
Duration of Subject Participation:	Clinical study participation for each subject is 3 weeks

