#### 4.2 Clinical Hypothesis

The Sponsor's test material will produce a statistically significant improvement in clinical grading of efficacy parameter scores over the course of 3 weeks of use when compared with baseline scores/values. Additionally, the Sponsor's test material will be well tolerated by the subjects, with no statistically significant increases in scores for tolerability/safety parameters at any study time point when compared with baseline scores. Furthermore, the Sponsor's test material will be well perceived by the subjects' parent/legal guardians according to a self-assessment questionnaire at day 1, week 1 and week 3, with a statistically significant proportion of favorable responses compared to unfavorable responses.

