### 5. OVERALL STUDY DESIGN

This is a single-center, open-label study to evaluate the efficacy and tolerability of a Healing Ointment when used on infants with mild-to-moderate diaper rash.

Protocol GLI.04.US.SL.023

CONFIDENTIAL

Subjects and their parent/legal guardians will report to the site at baseline (day 0) visit, will be given an informed consent form, HIPAA form, photography release form, and medical history form to complete.

Subjects will be screened on the basis of the selection criteria for study qualification. Efficacy assessment (skin health, skin smoothness, skin texture), and tolerability assessment (erythema, dryness, scaling, peeling, edema) will be performed, and baseline photographs will be taken.

Subjects' parent/legal guardians will be instructed to apply the provided Healing Ointment to the groin and buttocks area at every diaper change.

Subjects' parent/legal guardians will complete Day 1 questionnaire at home. Subjects and their parent/legal guardians to return to the site at day 7 ( $\pm 3$  days) and day 21 ( $\pm 3$  days) for follow-ups.

For each follow-up visit, Investigator will perform assessments and photography. Subjects' parent/legal guardians will perform self-assessment questionnaire.

A subject and their parent/legal guardian will be involved in the study for 3 weeks. The study visits are illustrated in **Error! Reference source not found.**

Protocol GLI.04.US.SL.023

CONFIDENTIAL

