**Table 5. Statistical Analysis Plan**

Evaluation	Change from Baseline	Notes/Interpretation
Efficacy Grading 

Skin smoothness (tactile)

Skin texture

Diaper dermatitis

	Paired t-test; If normality fails, a Wilcoxon signed-rank test will be used.	A decrease in scores indicates an improvement
Tolerability Grading 

Dryness

Peeling

Edema

	Paired t-test; If normality fails, a Wilcoxon signed-rank test will be used.	A decrease in scores or lack of significant increase indicates tolerability/safety of the treatment product
Self-Assessment Questionnaire	N/A	Percentage of favorable and unfavorable responses will be provided for each question

Questionnaires will be tabulated; and the frequency and percentage of all response options will be reported for each question and time point. For questionnaire inquiries without baseline response data, a binomial (sign) test will be performed to test if the proportion of the combined designated favorable responses is equal to the combined designated unfavorable responses for each applicable question. A higher percentage of favorable responses with a significant *p* value indicates positive subject perceptions of the study treatment.

Protocol Version: 01

This document contains confidential, proprietary information.

Protocol GLI.04.US.SL.023

CONFIDENTIAL

A more appropriate analysis may be performed, which will be recorded in biostatistics note to file and/or in the study report.

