**APPENDIX II: SELF-ASSESSMENT QUESTIONNAIRE****Day 1**

	Strongly agree 5	Agree 4	Neither agree nor disagree 3	Disagree 2	Strongly disagree 1
The product instantly soothes my baby's irritated skin					
I've noticed an instant relief on baby's irritated skin after applying the product					
My baby's skin feels smooth					
My baby's skin feels soft					

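### Two of the four Day 1 questionnaire items ask how the skin feels now, have no pre-product answer, and are still tested as evidence about the product

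*Combined protocol and SAP*

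**What the plan says.** **Hypothesis.** Section 4.2 expects a statistically significant excess of favorable over unfavorable answers on the "self-assessment questionnaire at day 1, week 1 and week 3". Parent satisfaction is a secondary objective (Synopsis; Section 4.1).

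**Items.** The Day 1 form in Appendix II has four items on a five-point agreement scale with a neutral middle. Two are about the product: whether it soothes at once, and whether relief was instant after applying it. The other two are about the skin: "My baby's skin feels smooth" and the same statement for softness. Appendix II has forms for Day 1, Visit 2 and Visit 3, and none for before first use.

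**Analysis.** Section 12.4 provides: "For questionnaire inquiries without baseline response data, a binomial (sign) test will be performed". The test compares the favorable with the unfavorable share. A significant p value with more favorable answers is taken as parents viewing the treatment well. Section 12.1 sets two-sided tests at 5%.

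**Timing.** The synopsis lists the questionnaire with the Day 0 site assessments: "tolerability assessment (dryness, peeling, edema), and self-assessment questionnaire will be performed". Section 5 leaves it out of that list and says instead that "parent/legal guardians will complete Day 1 questionnaire at home". Section 9.1.1 also has it done at home as a Day 1 form. Table 1 marks it in the Visit 1 column with the footnote "At home questionnaire after first application". Section 10.3 asks for it after first use and also at every visit.

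**The concern.** A sign test against 50% suits a question that is itself a judgement of the product. It does not suit a statement about the present condition of the skin. For such a statement, 50% agreement is not what one expects when the product does nothing. The expected share is whatever share of parents would have agreed beforehand, and the plan does not collect that.

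A parent whose baby's skin already felt soft, and who gives the same answer at Day 1, is counted in the product's favor. At stake is a false-positive route to part of the Day 1 hypothesis in Section 4.2, on two of the four items tested at that time point.

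A second, smaller matter is when the form is completed. The two items on instant effect depend on the time since application, and no section states that interval.

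**Working it through.** The plan gives no derived figure on this point, so there is nothing to reproduce first.

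**Inputs from the plan**
- Maximum 30 completers (Section 6.1)
- Two-sided tests at 5% (Section 12.1)
- Null hypothesis of equal favorable and unfavorable shares, p0 = 0.5 (Section 12.4)
- Four Day 1 items (Appendix II)

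**Assumptions**
- Neutral answers are left out of the sign test. The documents do not say how they are treated.
- The share q of parents with a non-neutral view who would agree before any product is set at 50% to 90%. The documents give no figure.
- The product does nothing, so Day 1 answers follow q.

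**Step 1: which items lack a pre-product answer.** All four do, since no pre-product form exists. The two items on instant effect ask about the product and could not have one. The two on smooth and soft skin could. The missing baseline is therefore a defect for two of four items.

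**Step 2: significance threshold.** Two-sided p = 2 × P(X ≥ k), with X ~ Binomial(n, 0.5). For n = 30:
- k = 20: p = 0.099
- k = 21: p = 0.043
- k = 24: p = 0.0014

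The test is significant from 21 of 30, that is 70%.

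**Step 3: chance of a significant favorable result with no product effect.** This is P(X ≥ k) with X ~ Binomial(n, q), where k is the threshold for that n.

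| Non-neutral answers n | Threshold k | q = 50% | 60% | 70% | 80% | 90% |
|---|---|---|---|---|---|---|
| 30 | 21 (p = 0.043) | 2% | 18% | 59% | 94% | >99% |
| 20 | 15 (p = 0.041) | 2% | 13% | 42% | 80% | 99% |

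Only at q = 50% does the test hold its nominal level (about 2% in the favorable direction). Above that, the chance of a favorable finding depends on how the skin felt before use.

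**Step 4: timing statements side by side.**

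| Place | When and where |
|---|---|
| Synopsis | With the Day 0 site assessments, ahead of the instruction to apply product |
| Section 4.2; Appendix II | Day 1, place not stated |
| Sections 5 and 9.1.1 | Day 1, at home |
| Table 1 | Visit 1 column; footnote: at home, after first use |
| Section 10.3 | After first use, and at every visit |

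All rows but the synopsis and the visit wording in Section 10.3 can describe one form: product dispensed at Day 0, first application, then the Day 1 form at home. No section says whether the first application falls on Day 0 or Day 1, or how long after it the form is due.

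**The case against.** The best defense is that the claim is modest. The plan speaks of parents' perception and satisfaction, a secondary objective. It openly provides for items without baseline data and reports the frequency of every response option. Change in smoothness is measured elsewhere, by investigator grading against baseline and by a Visit 2 item worded as a comparison. The 60% to 80% prior agreement has no basis in the documents, and infants enrolled with mild-to-moderate rash may well start lower. At 20 of 30 favorable the test is not significant.

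Most of this stands, and it limits the importance of the point. It does not rescue the test. Acknowledging that a baseline is absent does not make 50% the right null for a state item, and Section 12.4 still reads significance as an opinion of the treatment.

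A reader might infer more than the documents support:
- **That the items on instant effect fail for want of a baseline.** They ask about the product, so they cannot have one. Their limits are the unstated interval and the lack of a control.
- **That the schedule gives three rival time points.** The at-home, after-first-use and Day 1 statements are compatible. Only the synopsis, and loosely Section 10.3, depart from them.
- **That the synopsis already provides a pre-product questionnaire.** Appendix II contains no form that it could refer to.
- **That a baseline answer would let the change be credited to the product.** In an open-label study of one product without a control it would show change only.

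**Conclusion.** The point holds for the two Day 1 items on smooth and soft skin. Testing them against 50% does not separate a product effect from skin that already felt that way. With 30 non-neutral answers, the chance of a significant favorable result with no product effect is about 18%, 59% or 94% at assumed prior agreement of 60%, 70% or 80%. With 20 such answers it is 13%, 42% or 80%. These figures illustrate the mechanism; they do not estimate this trial's error rate, because the prior share is unknown.

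The synopsis and the visit wording in Section 10.3 need reconciling with the at-home form, and the completion interval needs stating. That part is a matter of missing detail.

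This is a worthwhile, inexpensive improvement to a secondary analysis. The primary efficacy and safety analyses do not depend on it.

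**What to change.** 1. Ask the smooth and soft items once at the Day 0 visit, before the first application, and add that short form to Appendix II and Table 1. In Section 12.4, replace the one-sample test for these two items with a paired analysis of the change to Day 1, for example an exact sign test of improved against worsened answers. State that this removes the already-soft artefact but does not by itself attribute the change to the product.
2. If no Day 0 answer is collected, report the two items as frequencies only, with no test-based claim about the product, and exclude them from the Day 1 hypothesis in Section 4.2.
3. State on which day the first application falls and one completion interval after it for the Day 1 form. Use the same wording in the Synopsis, Sections 4.2, 5, 9.1.1 and 10.3, Table 1 and Appendix II. Section 15.4 provides for electronic completion, so the time could be checked if the survey software records it.

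The cost is two extra questions at a visit already held, a paired analysis of two items, and wording changes. Option 2 costs wording only. The downside is that two secondary results may look less favorable, partly because parents who strongly agree at Day 0 have no room to improve.

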## 9.1 Visits

### 9.1.1. Visit 1 (Screening/Baseline / Day 0)

The following screening assessments will be performed:

- Obtain ICF, HIPAA form, and photography release form prior to conducting any study specific activity.

**Note:** Prior to beginning of any study related activities, subjects will be informed about the purpose and nature of the study, the expected post-treatment events, and the potential risks involved with the treatments. Once subjects have completed reading, they will be interviewed to ensure their understanding of the aforementioned forms and be given the opportunity to ask any study related questions. Subjects declining to sign any of the forms will be dismissed from the study.

- Assess eligibility: review inclusion/exclusion criteria. Subjects failing to meet criteria will be dismissed from the study.
- Record the subject's demographic information, medical history, and concomitant medications.

Once the subject is deemed eligible by the Investigator, the following procedures should be completed:

- Perform Clinical Grading and tolerability assessment as described in Section **Error! Reference source not found.** and 11.3.
- Digital photography will be completed as described in Section 10.2, if subject's parent/legal guardian consents.
- Dispense study product and diary. Instruct subject's parent/legal guardian on product application and diary completion. Remind subject's parent/legal guardian to complete the Day 1 questionnaire at home, and to bring the study products and diary to the next on-site visit.
- Schedule the next Visit 2 (Week 1).

### 9.1.2. Visit 2 (Week 1 ± 1 days)

- Confirm the subject's concomitant medications.
- Collect, weigh, and redistribute the study products.
- Collect, review, and distribute the diary.
- Interview subjects regarding any AEs that have occurred since starting study product application.
- Perform Clinical Grading and tolerability assessment as described in Section **Error! Reference source not found.** and 11.3.
- Digital photography will be completed as described in Section 10.2, if subject's parent/legal guardian consents.
- Instruct the subject to complete self-assessment questionnaire as described in Section 10.3.

Protocol GLI.04.US.SL.023

CONFIDENTIAL

- Schedule the next follow-up Visit 3 (Week 3  $\pm$  3 days).

#### 9.1.3. Visit 3 (Week 3 $\pm$ 3 days)

- Review the subject's concomitant medications.
- Collect, weigh, and retain the study products.
- Collect and review the diaries.
- Interview subjects regarding any AEs that have occurred since starting study product application.
- Perform Clinical Grading and tolerability assessment as described in Section **Error! Reference source not found.** and 11.3.
- Digital photography will be completed as described in Section 10.2, if subject's parent/legal guardian consents.
- Instruct the subject to complete self-assessment questionnaire as described in Section 10.3.
- Once completed, subjects will be dismissed from the Clinic.

## 9.2 Discontinued Subjects

Any subject is free to discontinue his/her participation in this study at any time and for whatever reason, specified or unspecified, and without prejudice.

An Investigator may decide to discontinue a subject from the study for safety reasons or when it is in the best interest of the subject. Galderma Laboratories, L.P. may also decide to prematurely terminate or suspend the study or the participation of a subject in the study. All data gathered on the subject prior to termination should be made available to Galderma Laboratories, L.P.

Criteria for the discontinuation of a subject during the study will include the following:

- Adverse Event
- Lack of Effect
- Pregnancy
- Subject Request
- Protocol Violation
- Lost to Follow-up
- Any unmanageable factor, in the Investigator's opinion, that may significantly interfere with the protocol or interpretation of results.

The reason and date for withdrawal should be documented in the subject's source documents and CRFs. When possible, an explanatory comment should be added to further explain the reason for the withdrawal. If withdrawal of a subject occurs during a regular study visit, the CRF for that specific visit shall be completed as far as possible.

If a subject is withdrawn from the study, all data collected until the time of withdrawal will be used in the analyses. Subjects who receive study products and are withdrawn or discontinued from the study will not be replaced. For AEs still ongoing at the time of withdrawal, see Section 13.

Protocol Version: 01

This document contains confidential, proprietary information.

## 10. EFFECTIVENESS ASSESSMENTS

The methods for collecting effectiveness data are described in this section. To minimize inter-observer variability, every effort should be made to ensure that preferably the same individual who makes the initial baseline assessments completes all corresponding follow-up evaluations.

The methods for collecting effectiveness data are:

- Efficacy Grading
- Self-Assessment Questionnaire
- Tolerability Grading

### 10.1 Clinical Grading by Investigator

Investigator will grade tactile smoothness and skin texture parameters using a 10-point Griffiths' scale where 0 = Excellent (best possible condition), 1-3 = Good, 4-6 = Fair, 7-9 = Poor (worst possible condition), as described in Table 2.

**Table 2. Grading Scale for Tactile Smoothness and Skin Texture**

Parameters	Excellent	Good			Fair			Poor		
	0	1	2	3	4	5	6	7	8	9
Skin Smoothness (tactile)	No palpable skin roughness, drag, and/or surface bumps, depressions	Mild palpable skin roughness, drag, and/or surface bumps, depressions			Moderate palpable skin roughness, drag, and/or surface bumps, depressions			Significantly (severe) palpable skin roughness, drag, and/or surface bumps, depressions		
Skin texture	Smooth visual skin texture	Slightly coarse and uneven skin texture			Moderately coarse and uneven skin texture			Severely coarse and uneven skin texture		

Investigator will grade diaper dermatitis parameter using a 5-point scale where 0 = Normal (no sign) and 4 = Severe (worst possible condition), as described in [Table 3](#).

